Research Study Protocol

Cover-Page

Study Title: Home-Based Dual-Task Training for Older Adults Date of Document: 02/07/2024 NCT#: NCT05108246

Study Protocol Title

Home-Based Dual Task Exercise for Older Adults

Investigative Team and Study Site

Principal Investigator: [name]

Co-Investigator: [name] MD

Study site

University at Buffalo, SUNY Jacobs School of Medicine and Biomedical Sciences

Research Synopsis

Title: Home-based Dual-Task Exercise for Older Adults

Clinical Phase: II

Study Population: Community-Dwelling adults, 65 years or older

Study Design: Two-group randomized controlled trial (RCT)

Sample Size: 30 participants are being sought for enrollment.

Study Duration: 12 months

Intervention Description: Home-based dual-task exercise training: combining aerobic exercise, balance training, strength, training, and simplified non-contact cardio kickboxing movements

Background and Significance:

Mild cognitive impairment (MCI) is an intermediate state between the cognitive decline expected with normal aging and more severe loss of cognition of Alzheimer's disease (AD) that effects more than 15% of older adults in the United States. MCI is associated with reduced attention, memory, physical functioning, as well as dualtask performance, and thus can be a significant burden to older adults.[1, 2] MCI also predicts AD with an annual conversion rate from MCI to AD equal to 15% in the United States.[3-5] Our rapidly aging society is ushering in a public health crisis for which we are not fully prepared. To better manage this approaching challenge and help preserve function and independence well into older age, we must develop and adopt innovative, evidence-based therapies that support cognitive and physical function in aging. Unfortunately, the COVID-19 pandemic has brought to the fore the need for effective and feasible therapies to help preserve function in the midst of the significant challenges posed by temporarily closed senior and recreation centers and the need for physical distancing that has isolated many older adults at home. Our team has demonstrated success in developing, implementing, and evaluating a community-based intervention to improve cognition and physical function in an older adult population.

The underlying neurophysiological mechanisms of improved cognition in response to dual-task exercise training have not been fully characterized. However, there is evidence that dual-task exercise stimulates essential, adaptive neurobiological processes eliciting a widespread response. Previous studies demonstrate that these adaptations correlate with better outcomes in older adults both with and without cognitive impairment.[9-16] Exercise and cognitive stimulation increase cerebral blood flow[9], improve brain plasticity, and preserve hippocampal volume. [10-12, 14- 17], all of which are important factors in maintaining cognitive and motor function as we age.

Study Objectives

Primary Objective

The main purpose of conducting this study is to assess the therapeutic benefits of a home-based dual-task exercise intervention on functional capacity in older adults, aged 65 years or older with mild cognitive impairment. To do so, a 12-week dual-task exercise program will be delivered via pre-recorded videos accessed by tablet computer. Baseline and endpoint assessment of physical function (balance, walking, and lower-body strength) will be conducted to compare changes in function between intervention and control participants.

Secondary Objectives

The secondary purpose of conducting this study is to assess the therapeutic benefits of a home-based dualtask exercise intervention on functional capacity in older adults, aged 65 years or older with mild cognitive impairment. To do so, a 12-week dual-task exercise program will be delivered via pre-recorded videos accessed by tablet computer. Baseline and endpoint assessment of cognitive function (task-switching, memory, interference inhibition, and attention) will be conducted to compare changes in function between intervention and control participants.

Study design/methodology

This is a randomized controlled pilot trial to investigate the therapeutic impacts of home-based dual-task exercise on physical and cognitive function among older adults, 65 years or older with mild cognitive impairment. Study arms include one intervention group receiving a 12-week exercise-based intervention and one control group receive no exercise intervention.

A total of 30 participants will be sought for enrollment, recruited from senior living communities, recreation centers, and other areas in which older adults congregate, via flyers and informational sessions. Once enrolled, participants will be randomly assigned to either control or intervention group. Baseline

measures will be completed among all participants prior to initiation of any intervention activities. At baseline physical function will be assessed using the Four-Stage Balance Test, the 30-Second Sit to Stand Test, and aerobic fitness will be assessed using the Six-Minute Walk Test. Cognitive function will be assessed using the Stroop Color-Word Test and Trail-Making Test A and B.

For participants in the intervention group, a 12-week home-based program will be delivered by computer tablet within each participant's home. Each participant will be loaned a tablet and stand and small exercise equipment (resistance bands, light dumbbells, and a body-bar). Two exercise sessions will be completed weekly on non-consecutive days for the duration of the program. To access videos, participants will log in to a password protected Vimeo site. For participants in the control group, no changes to current exercise habits will be made for the duration of the 12-week program. Upon completion of the 12 weeks, all participants will complete endpoint assessments that will be identical to the baseline assessments (physical and cognitive functions).

Study Participants

Inclusion Criteria: 1) male or female, 2) mild cognitive impairment with a score on the Montreal Cognitive Assessment 23 - 26 points, 3) > 65 years of age, 4) healthy enough for home-based physical activity as screened using the Physical Activity Readiness Scale for Older Adults.

Exclusion Criteria: 1) Having any condition that prevents safe participation in the physical activity component as screened using the Physical Activity Readiness Questionnaire for Older Adults; 2) likelihood of 4 withdrawing due to presence of severe illness; 4) having any amputation; 5) inability to provide informed consent, 6) Having a score of less than 15 points on the UBACC. Importantly, in reviewing and signing the consent form, the participant's score on the UBACC will be reviewed with the participant and ability to consent will be discussed to ensure the participant understands that they possess the ability to consent.

Informed Consent Process

Participants must provide written informed consent for data collection related to safety and outcomes assessments. Only data elements specific in this protocol will be collected. This study does not require a review of the medical record for data collection purposes. Consent procedures will be conducted in-person at the first measurement session prior to completion of any research-related activities. The research assistant on this project of the project director will conduct the consent process.

Each participant will be provided with a written consent form detailing the expectations for participation in the study. Each participant will be asked to read the consent form carefully and then the consenter and participant will review the consent form verbally together to ensure complete understanding of the research process. Questions or concerns will then be addressed by the consenter. If comfortable, the participant will sign and date the form, followed by the consenter.

Privacy and Confidentiality

Privacy and confidentiality: Data will be electronically stored on a University at Buffalo-owned, password protected desktop computer using a password protected Microsoft Access file, in the locked office of [name]. Data for the proposed study will be stored, coded with randomly assigned identification numbers. Data for this project will be stored for three years. Only [name], in the Department of Medicine, will have access to the key linking participant information to participant identification. This key will be stored in a separate electronic file folder for all study data using a password protected Microsoft Access File on a passwordprotected desktop computer in [name] locked office.

Intervention Description:

The intervention being tested consists of two days per week of dual-task exercise training delivered by prerecorded videos posted on a password protected Vimeo site. Participants in the intervention group will participate in an exercise program consisting of balance and strength training, non-contact cardio kickboxing movements, stepping and walking, combined with frequent changes to instructions to engage both mind and body, simultaneously.

Overall Study Duration: 12 weeks

Study Arms: Participants will be randomly assigned to either intervention, as described above, or control

Control: Participants receive no guided dual-task exercise; instructed to not make any changes to their physical activity and exercise habits for the 12-week study duration.

Intervention: Participants receive two non-consecutive days per week of guided dual-task exercise. Sessions are 40 minutes in length with warm-up and cool-down.

Outcomes Measurement

Primary Objective

The main purpose of conducting this study is to assess the therapeutic benefits of a home-based dual-task exercise intervention on functional capacity in older adults, aged 65 years or older with mild cognitive impairment. To do so, a 12-week dual-task exercise program will be delivered via pre-recorded videos accessed by tablet computer. Baseline and endpoint assessment of physical function (balance, walking, and lower-body strength) will be conducted to compare changes in function between intervention and control participants.

Functional Capacity Measures

- Change in performance on the Four-Stage Balance Test (baseline to end point)

A Modified Four-Stage Balance Test is a literature-validated assessment of fall risk. It is based on the person's ability to hold four progressively more difficult stances for a duration of 10 seconds: side-by-side, tandem, left leg, and right leg. This test will be administered at baseline and end point.

- Change in performance on the Six-Minute Walk Test (baseline to end point)

The Six-Minute Walk Test will be used to assess changes in walking speed from baseline to end point. This assessment is a literature-validated test of physical function in older adults. Scoring is based on distance covered in in six minutes. This test will be administered at baseline and end point.

Secondary Objectives

The secondary purpose of conducting this study is to assess the therapeutic benefits of a home-based dualtask exercise intervention on functional capacity in older adults, aged 65 years or older with mild cognitive impairment. To do so, a 12-week dual-task exercise program will be delivered via pre-recorded videos accessed by tablet computer. Baseline and endpoint assessment of cognitive function (task-switching, memory, interference inhibition, and attention) will be conducted to compare changes in function between intervention and control participants.

Cognitive Function Measures

- Change in performance on the Stroop Color-Word Test (baseline to endpoint)

The Stroop Color Word Test will be administered at baseline and end point to assess interference inhibition, task-switching, and attention. This assessment is valid among older adults with mild cognitive impairment.

- Change in performance on the Trail-Making Test (baseline to end point)

The Trail-Making Test parts A and B will be administered at baseline and end point to measure attention and working memory. It is a valid test for older adults with mild cognitive impairment.

Study Schedule

Projected Start Date: 12/15/2021.

Intervention Duration: 12 weeks

Study Duration: (planning, recruitment, intervention): 12 months

Study End Date: 12/31/2022

Study Timeline

- 1) Planning and Content Development: 09/01/2021 11/15/2021
- 2) Recruitment and Enrollment: 09/01/2021 05//21/2022
- 3) Baseline Assessment: 06/15/2022 07/05/2022
- 4) Intervention: 07/10/2022 10/10/2022
- 5) End Point Assessment: 10/05/2022 10/20/2022

Statistical Analysis Plan

Due to limited sample size and in response to a non-normal distribution, the key measure central tendency (Median) will be assessed along with interquartile range. Differences between intervention and control in median change scores will then be assessed quantitatively.

Change in physical and cognitive measures between intervention and control will be assessed first with calculation of a change score between baseline and endpoint for each group (intervention and control). These change scores will then be compared statistically using a separate Mann-Whitney U test (Median with interquartile range) for each outcome. Due to the small sample size, the ability to make deeper comparisons is very limited.

Risk/Benefit:

Limited risks to participants are associated with participation in non-physician supervised physical activity programming. These are: falls, musculoskeletal injury including strained muscles or joints that are frequently temporary and resolve on their own. Other minor risks include lightheadedness, exercise induced fatigue and diaphoresis, which will resolve on their own upon termination of the exercise challenge. Serious cardiovascular risks include sudden cardiac death, myocardial infarction, and stroke during exercise. These risks often significantly impact the health of the participant and the impacts of which are not fully reversible. However, serious adverse effects of exercise participation are very rare.

From the American College of Sports Medicine: "Contemporary estimates of major cardiovascular

complications in exercise-based cardiac rehabilitation programs range from 1/100,000 to 1/300,000 participant exercise hours. Thus, exercise rehabilitation has been shown to be safe with serious events being rare. Moreover, the overall risk of a cardiac event appears to be reduced in persons who are regular exercisers".

There are no known direct benefits to participants in this study.

Data Safety Monitoring

Data safety monitoring will be conducted throughout this investigation by the PI. Weekly review and interim analyses of both safety and outcomes data will be conducted to monitor participant safety throughout the intervention. This will include both an ongoing quantitative review of adverse events and a qualitative assessment of participant experience in the intervention.

Adverse Event Reporting

Case report forms will be used for review and reporting of safety data. Prior to engaging in intervention activities, participants will be screened for safe physical activity participation using the PAR-Q for Older Adults. These data will be collected on an intervention data sheet and reviewed by the PD. Adverse events during the physical activity sessions will be recorded on the intervention data sheet for each participant and compiled into an Access Database.

Adverse event data collection will be performed monthly by direct contact with participants. Management strategies will be primary in pre-screening of participant risk via the Physical Activity Readiness Questionnaire for Older Adults. Non-serious adverse events that might occur include musculoskeletal pain, joint sprains / strains, lightheadedness, fatigue, shortness of breath, and overexertion. Serious adverse events include falls, syncope, sudden cardiac death, myocardial infarction, and cerebrovascular accident. Occurrence of a serious adverse event including hospitalization, myocardial infarction, sudden cardiac death, cerebrovascular accident, fracture, or death, that the PI determines might be research-related, will trigger an immediate suspension. In addition, any changes to the risk / benefit profile of the study determined by the literature, interim results, or other findings that indicate unexpected changes to the risks and potential benefits of the study will trigger a suspension. The PI reserves the right to suspend the research if any previously unforeseen event or problem presents risks to the participants.

References:

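### No allocation ratio or restriction is stated for 30 participants, and the unadjusted change-score test corrects a chance baseline gap in walking only in part

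*Combined protocol and SAP*

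**What the plan says.** The section Study design/methodology sets the size, "A total of 30 participants will be sought for enrollment", and the allocation, "Once enrolled, participants will be randomly assigned to either control or intervention group". The Study Arms paragraph under Intervention Description repeats it: "Participants will be randomly assigned to either intervention, as described above, or control". Neither place gives a ratio, a method of generating the sequence, blocks, strata or concealment.

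On timing, Study design/methodology says that baseline "measures will be completed among all participants prior to initiation of any intervention activities". The Study Timeline lists "2) Recruitment and Enrollment: 09/01/2021 05//21/2022" and then "3) Baseline Assessment: 06/15/2022 07/05/2022", and opens the intervention on 07/10/2022. Informed Consent Process, however, places consent at the first measurement session. The order of enrolment, allocation and baseline testing is therefore not settled.

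The Six-Minute Walk Test is one of the two measures listed for the primary objective under Outcomes Measurement. For the analysis, the Statistical Analysis Plan takes endpoint minus baseline and says: "These change scores will then be compared statistically using a separate Mann-Whitney U test", one for each outcome. No baseline covariate or stratum enters the test.

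**The concern.** With 30 people, chance alone can leave the arms unequal in size and in starting fitness. The plan describes nothing in the design to prevent this. In the analysis, baseline is only subtracted. People who start low tend to gain and people who start high tend to lose, because baseline and endpoint are not perfectly correlated. A gap in baseline walking therefore leaves a residue of opposite sign in the comparison of changes. In a single small trial that residue is a ready rival explanation for any difference seen.

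The schedule offers a way to prevent it. The cohort is handled as one batch, and all walk distances are due by 07/05/2022, five days before the intervention opens. The whole group could be allocated in one step, balanced on a measure already being collected.

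**Working it through.** **Inputs from the documents.** N = 30, two arms, an unadjusted Mann-Whitney test on change, and the dates above. The target of 30 has no derivation, so there is no planned power to reproduce.

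**Assumptions, since the documents give no values.** Simple 1:1 assignment; two-sided 5% level; normal data with equal baseline and endpoint SD; no dropout unless stated; baseline-endpoint correlation ρ from 0.5 to 0.9. Effects are in SDs of walk distance.

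**1. Arm sizes.** With X ~ Binomial(30, 0.5):
- 19:11 or worse: 2·P(X ≥ 19) = 0.200.
- 20:10 or worse: 2·P(X ≥ 20) = 0.099.
- Cost in standard error at 19:11: √[(1/19 + 1/11)/(2/15)] = 1.038, or 3.8%. Averaged over all splits it is 1.8%.

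Unequal arms alone are thus a minor loss.

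**2. Baseline walk gap.** At 15:15 the difference in means has SD √(2/15) = 0.365. Then P(|gap| > 0.5) = 2·[1 − Φ(0.5/0.365)] = 0.171. Simulation under simple assignment, where the arms also vary in size, gives about 18%. A fixed 15:15 split alone leaves it at about 17%. Three strata of ten ranked on baseline walk, 5:5 in each, cut it to about 0.4%.

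**3. What subtraction leaves behind.** The shift in the change contrast is (ρ − 1) × gap. For a gap of 0.5 SD:

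| ρ | shift (SD) |
|---|---|
| 0.5 | −0.25 |
| 0.7 | −0.15 |
| 0.8 | −0.10 |
| 0.9 | −0.05 |

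So 10% to 50% of the gap passes through, with reversed sign.

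**4. Variance.** With arms of 15, the difference in mean change has variance 2(1 − ρ)·(2/15). With baseline fully balanced it is (1 − ρ²)·(2/15). The ratio is (1 + ρ)/2.
- ρ = 0.6: 0.107 against 0.085, ratio 0.80. Simulated, simple against three strata: 0.110 against 0.090.
- ρ = 0.8: 0.053 against 0.048, ratio 0.90. Simulated: 0.055 against 0.0495.

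**5. Power for the walk outcome, effect 0.8 SD** (simulated; repeat runs differ by about a point):

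| ρ | simple assignment, Mann-Whitney | three strata, van Elteren |
|---|---|---|
| 0.6 | about 61% | about 69% |
| 0.8 | about 89% | about 91% |
| 0.9 | about 99% | about 99% |

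The SD of change is √[2(1 − ρ)], which is 0.89, 0.63 and 0.45 in the three rows. The same 0.8 SD effect is thus 0.89, 1.26 and 1.79 SDs of change, and at ρ = 0.9 there is no power left to gain.

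**6. Type I error.** Simple assignment with Mann-Whitney gives about 4.5% to 5%; strata with van Elteren 5.0% to 5.3%. Over repeated randomisations the simulated mean effect under no treatment difference is about zero.

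**7. Other outcomes.** Using walk strata in the test of a different outcome gives no gain, and loses up to about 5 points of power with 15% dropout.

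**The case against.** **The method is not stated.** A reader might infer from the wording that assignment is unrestricted. The documents do not say so; an unreported 15:15 or blocked list fits the text equally well. This stands, and the probabilities in steps 1 and 2 are conditional on simple assignment. A fixed split would remove the first set but leave the baseline gap almost unchanged.

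**Baseline may not be known at allocation.** A reader might also infer that walk results are already available when people are assigned. The text ties assignment to enrolment, and the timeline closes enrolment before baseline testing opens, while the consent section points the other way. This stands too: the fix has to set the timing of allocation, not only its method.

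**The analysis could do the same work.** Under simple assignment, baseline-adjusted linear regression reached 73% power at ρ = 0.6 and 92% at 0.8, against 70% and 91% for strata with van Elteren in the same simulation. This is a fair point and offers a route if allocation cannot be moved. But the Statistical Analysis Plan chooses rank methods because it expects non-normal data, and the regression figures assume normality.

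**Much of the power gain comes from the test.** At ρ = 0.6, stratified allocation with the planned Mann-Whitney test gives 65%, against 64% for a fixed 15:15 split and 62% for simple assignment. With strata and no matching test, type I error falls to about 3%, so the balance is paid for but not used. The two changes belong together.

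**It is a pilot.** The protocol calls it one and admits that comparisons are limited. That lowers the weight of the point. It does not remove the case for a change of a few lines.

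**Conclusion.** The point holds as a gap in the allocation plan combined with an analysis that uses baseline only by subtraction. If assignment is simple, 20% of such trials would split 19:11 or worse, and about 18% would start with a walk gap above 0.5 SD. A gap of 0.5 SD would move the change contrast by 0.05 to 0.25 SD.

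It would be tempting to read this as bias or an inflated false-positive rate. The calculations do not support that: type I error stays at or just below 5% and the average effect is unbiased. The harm is lost precision, and chance imbalance in the one trial that is run.

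The benefit of the fix is real but depends on a correlation that the documents do not give: about 8 points of power at 0.6, about 2 at 0.8 and none at 0.9. These figures assume normal data, no dropout and an effect of 0.8 SD, and they apply to walking only.

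**What to change.** **Protocol, Study design/methodology and Study Arms.** State that allocation takes place after the last baseline test, in one computer-generated draw with equal arms. Rank participants on baseline six-minute walk distance into three strata. If 30 enrol, these are three strata of ten, allocated 5:5. Otherwise use strata of the nearest even size; an odd total leaves one stratum uneven by one. Reconcile the enrolment and consent wording with this order.

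**Statistical Analysis Plan.** For the walk outcome, replace the plain Mann-Whitney test with van Elteren's test using the same strata. Keep the planned Mann-Whitney test for the other outcomes.

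**Cost.** A few lines, with no new visits or data. Allocation becomes known only after baseline closes, so the draw, the notification of participants and the lending of equipment must fit between 07/05 and 07/10/2022. Balance is secured on walking only, and dropout reduces the gain.

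**If allocation has already taken place.** The cover page is dated after the planned end of the study, so this is possible. In that case, report the method, ratio and timing actually used, and add a baseline-adjusted analysis of the walk outcome, stating when it was decided.

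### The protocol does not say who runs the baseline and endpoint tests or that testers are unaware of allocation, so tester knowledge could bias the change scores

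*Combined protocol and SAP*

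**What the plan says.** **Allocation and comparator.** Under Study design/methodology, "A total of 30 participants will be sought for enrollment" and "Once enrolled, participants will be randomly assigned to either control or intervention group". There is "one control group receive no exercise intervention". Baseline testing must precede intervention activities, but it is not said to precede randomisation.

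**Testing.** At the end of the 12 weeks "all participants will complete endpoint assessments that will be identical to the baseline assessments". Outcomes Measurement describes the tests. For the six-minute walk, "Scoring is based on distance covered in in six minutes". The balance test rests on the "ability to hold four progressively more difficult stances for a duration of 10 seconds". Stroop and Trail-Making are given at baseline and endpoint. The 30-second sit-to-stand is listed as a baseline test under Study design/methodology but does not appear among the outcome measures in Outcomes Measurement. No section names a tester, gives an administration script or mentions masking.

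**Staff.** The Informed Consent Process section says "The research assistant on this project of the project director will conduct the consent process" (the word *of* is probably a slip for *or*). A principal investigator (PI) and a co-investigator are also listed. The intervention is "dual-task exercise training delivered by prerecorded videos posted on a password protected Vimeo site". Data Safety Monitoring has the PI reviewing safety and outcome data each week. Adverse Event Reporting has a person abbreviated PD reviewing screening data held on the intervention data sheet, and provides for monthly contact with participants.

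**Analysis.** The Statistical Analysis Plan compares change scores between arms with a separate Mann-Whitney U test for each outcome.

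**The concern.** All of these are performance tests given by a person. How the task is explained, how much the participant is urged on, and when a stopwatch is started or stopped can each affect the score. A tester who knows that one person has trained for 12 weeks and another has not may, without intending to, treat them differently. Participants know their own arm, so the tester is the one party at the visit who could be kept unaware.

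At stake is the primary comparison. A tester effect that differs by arm has the same form as a treatment effect, and the planned analysis cannot tell them apart. The stated purpose is to assess therapeutic benefit, so calling the trial a pilot does not remove the issue.

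**Working it through.** **1. Is there any masking provision?** The sections that could contain one were read side by side.

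- Study design/methodology: random assignment, with no masking and no tester named.
- Outcomes Measurement: what each test is and when it is given, not by whom.
- Privacy and Confidentiality: coded identification numbers and a restricted key. These protect identity in stored data. They do not hide the arm from someone testing a participant face to face.
- Data Safety Monitoring: weekly review of outcome data by the PI, not stated to be masked.
- Statistical Analysis Plan: nothing on masking.

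The provision is absent.

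**2. How a tester effect reaches the result.** The change score is endpoint minus baseline. If the tester adds an average amount *b* to endpoint scores in the intervention arm relative to control, the expected between-arm difference in change is the true effect plus *b*. Enlarging the trial does not shrink *b*. Because randomisation may precede baseline testing, the baseline score is not clearly protected either.

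**3. Illustration of size.** The plan gives no figure to reproduce: it states no alpha, SD, effect size or allocation ratio. The assumptions are:

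- 30/2 = 15 per arm (1:1 assumed), with 12 per arm as a sensitivity case;
- normal change scores with SD 1 and no true effect;
- two-sided Mann-Whitney test at 5%;
- tester shift *b* of 0, 0.2, 0.3 or 0.5 SD of change.

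Simulated rejection rates, 20,000 trials per setting:

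| *b* (SD) | 15 per arm, any rejection | 15 per arm, favouring intervention | 12 per arm, favouring intervention |
|---|---|---|---|
| 0 | 4.4% | 2.2% | 2.3% |
| 0.2 | 7.2% | 6.6% | 6.0% |
| 0.3 | 11.1% | 10.8% | 9.2% |
| 0.5 | 23.6% | 23.5% | 19.2% |

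A separate simulation of 6,000 trials per setting at 15 per arm gave 4.2%, 7.1%, 11.2% and 23.9% for any rejection.

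Cross-check by normal approximation, one direction: Φ(b√(n/2) − 1.96). With n = 15, √7.5 = 2.739.

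- b = 0.2: Φ(0.548 − 1.96) = Φ(−1.412) = 7.9%
- b = 0.3: Φ(0.822 − 1.96) = Φ(−1.138) = 12.7%
- b = 0.5: Φ(1.369 − 1.96) = Φ(−0.591) = 27.7%

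This approximates a test of means and runs somewhat above the simulated rank test, as expected. For a fixed *b* the rate is higher at 15 than at 12 per arm, so the problem is not caused by small numbers.

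**4. Who could be masked?** Sessions are recorded videos, so no one has to lead them. If PD means project director, that person reviews the intervention data sheets, and the PI sees outcome data weekly. That leaves the research assistant as the most plausible masked tester, provided others take on the tasks that reveal the arm. On load, the timeline sets endpoint testing from 10/05/2022 to 10/20/2022. That is 16 days for 30 people, and 30/16 is about 1.9 per day.

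**The case against.** **The figures rest on invented shifts.** This is right. The documents give no SD and no estimate of tester bias, so the table is in effect the power curve of the test. The Statistical Analysis Plan chose rank methods because the data are not normal, and the balance test is capped at four 10-second stances, so a continuous normal shift fits it poorly. The figures show what a bias of a given size would do, not what size it has here.

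**Existing staff may not be enough.** A reader might infer from the two named roles and the recorded sessions that no further assessor is needed. The documents do not establish that. The staffing sentence is garbled, no section assigns randomisation, tablet loans, adverse-event contacts or testing to anyone, and the project director might also be the PI. The research assistant is a reasonable candidate, but only by inference.

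**Silence is not evidence of unmasked testing.** A reader might also infer that the tests were run by people who knew the allocation, or that the result is biased. The documents show only that nothing prevents this.

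**Masking the tester is a partial remedy.** This also stands. Participants know their arm and may try harder or less hard because of it.

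**The trial is a small pilot, and its testing window is past.** The Statistical Analysis Plan already concedes limited comparisons, and the document is dated 02/07/2024, after the scheduled October 2022 testing. This may change the remedy from prevention to disclosure. It does not make the information unnecessary for reading the result.

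**Conclusion.** The point holds as a risk of bias that the plan leaves open. The protocol neither names the testers nor masks them, and the tests it relies on can be influenced by whoever gives them. This affects the primary physical outcomes and the secondary cognitive ones. Sit-to-stand is affected too, if it is analysed as an outcome.

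The size is unknown. Under the stated assumptions, a tester effect of 0.2 to 0.5 SD of change would raise the false-positive rate from about 4% to about 7-24%, almost all of the excess favouring the intervention. This is a conditional range, not an estimate for this trial. The design gap does not depend on any one value in it.

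**What to change.** **If testing is still to come**, add a paragraph to Study design/methodology stating that:

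- one existing team member, most plausibly the research assistant, runs the endpoint tests;
- that person has no access to the allocation list, tablet and equipment loans, intervention data sheets, monthly adverse-event contacts or the weekly outcome review, which are handled by the project director or PI;
- one fixed instruction and encouragement script is used at baseline and endpoint;
- participants are asked not to reveal their group, and the assessor records a guess of allocation after testing, so that failures of masking can be reported.

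**If testing is complete**, report who tested at each visit and whether they knew the allocation. If they did, or if it cannot be established, limit the efficacy conclusion accordingly.

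**Cost.** A paragraph, a script and a division of duties, with no change in sample size or analysis. Scheduling becomes less flexible, the project director or PI takes on more participant contact, and some participants will still reveal their arm. If the team cannot be divided in this way, a further assessor would be needed. Differential effort by participants is not addressed and should be acknowledged as a limitation.
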